## 2.3 Study Design

This is a multicenter, open label, Phase 2 study, with 3 parallel cohorts. The aim of the study is to evaluate the efficacy of:

- a) APX005M administered at 2 different schedules to adult subjects with unresectable or metastatic melanoma who have not received prior immunotherapy. Enrolled subjects will be alternately assigned to one of the following 2 cohorts as long as both cohorts are open:

**Cohort 1:** APX005M administered IV at 0.3 mg/kg every 3 weeks (21-day cycle)

**Cohort 2:** APX005M administered IV at 0.3 mg/kg every 2 weeks (14-day cycle)

The intent of the alternating cohort assignment is to maintain approximately the same number of treated subjects in each of these 2 cohorts at any given time. Therefore, enrolled subjects assigned to Cohorts 1 or 2 who do not receive APX005M or are not evaluable for tumor response will be replaced in that cohort before assigning new subjects to the other cohort.

- b) APX005M in combination with stereotactic body radiation therapy (SBRT) in adults with unresectable or metastatic melanoma who have failed approved immunotherapy regimens:

**Cohort 3:** APX005M administered IV at 0.3 mg/kg in combination with radiation therapy every 2 weeks (14-day cycle) up to 16 weeks followed by APX005M administered IV at 0.3 mg/kg every 2 weeks (14-day cycle).

Subjects in all 3 cohorts with unconfirmed PD (iUPD, iRECIST) will be permitted to continue treatment as long as they meet the criteria in Section (3.2.6.2 Treatment beyond Progression)

- a. Investigator-assessed clinical benefit, without rapid disease progression, or with disease progression based primarily on changes in lymph nodes appearance
- b. Subject continues to meet retreatment criteria
- c. Subject tolerates study treatment
- d. Subject has stable ECOG performance status
- e. Treatment beyond progression will not delay an imminent intervention to prevent serious complications of disease progression (e.g., CNS metastases).

They do not have confirmed PD as defined by iRECIST on a repeated tumor assessment 4-8 weeks later.

### Study periods:

For every subject the participation in the study consists of 3 periods: Screening Period, Treatment Period, and Follow-up Period.

#### Screening period:

All subjects signing the informed consent form will enter the Screening Period

#### Treatment period:

Treatment period will start with the administration of 1st dose of APX005M ± SBRT and will continue for up to 12 months or until criteria Section 3.2.6.1 (Discontinuation of subjects from treatment) are met.

#### Follow-up period:

Subjects who discontinue APX005M will enter the Follow-up Period unless treatment discontinuation is due to withdrawal of consent for all study procedures, initiation of any anticancer therapy (except for subjects continuing immediately following this study on a PD-1/PD-L1 containing regimen for whom the regimen and the response to that regimen should be documented), subject lost to follow-up, death, or study termination by Apexigen.

Tumor responses will be evaluated approximately every 8 weeks following the first dose of APX005M. Subjects that discontinue treatment before the first scheduled on-study tumor assessment (8 weeks following the first dose of APX005M) should have the tumor response evaluated at the end of treatment visit. Subjects that are non-evaluable for tumor response will be replaced.

### **2.3.1 Eligibility and Randomization**

This is an open-label study in three Parallel cohorts and there is no randomization or blinding needed.

## 2.3.2 Eligibility Criteria

### 2.3.2.1 Inclusion Criteria

1. Histologically or cytologically confirmed unresectable or metastatic melanoma
2. Subjects with BRAF activating mutation must have received a BRAF inhibitor and/or MEK inhibitor regimen prior to study entry
3. Signed written informed consent approved by the relevant local ethics committee(s)
4. Male or female  $\geq 18$  years old at time of consent
5. Measurable disease by RECIST 1.1
  - a. For Cohort 3 only, subjects must have at least 3 measurable non-CNS target lesions
6. ECOG performance status of 0 or 1
7. Resolution of all disease or prior treatment-related toxicities to Grade  $\leq 1$ , with the exception of alopecia, Grade 2 neuropathy and laboratory abnormalities (parameters below apply). If subject received major surgery or radiation therapy of  $>30$  Gy, they must have recovered from the toxicity and/or complications from the intervention
8. Adequate organ function within 14 days prior to first dose of investigational therapy(ies):
  - a. WBC  $\geq 2 \times 10^9/L$  in absence of growth factor support
  - b. ANC  $\geq 1.0 \times 10^9/L$  in absence of growth factor support
  - c. Platelet count  $\geq 100 \times 10^9/L$
  - d. Hemoglobin  $\geq 9$  g/dL
  - e. Serum creatinine  $\leq 1.5$  mg/dL
  - f. Calculated (using the formula of local laboratory) or measured creatinine clearance  $\geq 60$  mL/min
  - g. AST and ALT  $\leq 2.5 \times$  ULN
  - h. Total bilirubin  $\leq 1.5 \times$  ULN, or direct bilirubin  $\leq$  ULN for subjects with total bilirubin levels  $>1.5 \times$  ULN
  - i. INR or PT  $\leq 1.5 \times$  ULN unless subject is receiving anticoagulant therapy as long as PT or PTT is within therapeutic range of intended use of anticoagulants
  - j. aPTT  $\leq 1.5 \times$  ULN unless subject is receiving anticoagulant therapy as long as PT or PTT is within therapeutic range of intended use of anticoagulants
9. Women of childbearing potential (WOCBP) must have a negative serum pregnancy test within the 7 days prior to first dose of investigational therapy(ies) and a negative urine pregnancy test within the 3 days prior to first dose of investigational therapy(ies), or a negative serum pregnancy test within the 3 days prior to first dose of investigational therapy(ies)
10. Women of childbearing potential must agree to follow instructions for method(s) of contraception for the duration of study treatment and 5 months after the last dose of investigational therapy(ies). Males who are sexually active with WOCBP must agree to follow instructions for method(s) of contraception for the duration of study treatment and 7 months after the last dose of investigational therapy(ies)

11. Available archived or fresh tumor tissue sample for biomarker analysis. Note: For Cohort 3, only available archived tissue is required.
12. For subjects that consent to collection of tumor biopsies at study entry and before the first scheduled tumor assessment, primary or metastatic tumor that can be safely biopsied. Up to 18 subjects (6 subjects within each cohort) should consent to fresh core biopsies.

### 2.3.2.2 Exclusion Criteria

1. Prior Therapy:
  - a. Cohorts 1 and 2 only: Previous exposure to any immunomodulatory agent (such as CTLA-4, PD-1/PD-L1, IDO inhibitors, interferon, CD40 agonist etc.).
  - b. Cohort 3 only: Prior therapy with a CD40 agonist. Any number of prior lines of therapy are eligible. A minimum washout period of 21 days from last line of therapy until investigational therapy(ies) administration should be observed
2. Second malignancy (solid or hematologic) within the past 3 years except locally curable cancers that have been apparently cured, such as basal or squamous cell skin cancer, superficial bladder cancer, or carcinoma in situ of the prostate, cervix, or breast
3. Active, known, clinically serious infections ( $\geq$  Grade 2 according to NCI-CTCAE v4.03) within the 14 days prior to first dose of investigational therapy(ies)
4. Use of systemic corticosteroids or other systemic immunosuppressive drugs within 28 days prior to first dose of investigational therapy(ies) (except inhaled corticosteroids)
  - a. The use of physiologic doses of corticosteroids may be approved after consultation with the Apexigen Medical Monitor (or designee)
5. Major surgery within 4 weeks prior to first dose of investigational therapy(ies)
6. Concurrent treatment with any anticancer agent (except for hormonal therapy) and palliative radiation, unless approved by the Apexigen Medical Monitor (or designee)
7. History of allogeneic bone marrow transplantation
8. Active, known or suspected autoimmune disease
9. Active autoimmune disease that has required systemic treatment in past 2 years (i.e. with use of disease modifying agents, corticosteroids or immunosuppressive drugs). Subjects with Type 1 diabetes mellitus, hypothyroidism only requiring hormone replacement, skin disorders (such as vitiligo, psoriasis, or alopecia) not requiring systemic treatment, or conditions not expected to recur in the absence of an external trigger are permitted to enroll
10. History of (non-infectious) pneumonitis that required corticosteroids or current pneumonitis
11. History of interstitial lung disease
12. History of sensitivity or allergy to mAbs or IgG
13. Congestive heart failure (New York Heart Association Class III to IV), symptomatic ischemia, conduction abnormalities uncontrolled by conventional intervention, or myocardial infarction within 6 months prior to the first dose of investigational therapy(ies)

14. History of any thromboembolic event within 3 months prior to first dose of investigational therapy(ies) or active coagulopathy
15. Known active central nervous system (CNS) metastases and/or carcinomatous meningitis. Subjects with untreated brain metastases ≤3mm that are asymptomatic, do not have significant edema, cause shift, and do not require steroids or anti-seizure medications are eligible after discussion with the Medical Monitor. Lesions of any size in posterior fossa are excluded. Subjects with previously treated brain metastases may participate provided they are stable after treatment (without evidence of progression by imaging for at least 4 weeks prior to the first dose of trial treatment and any neurologic symptoms have returned to baseline), have no evidence of new or enlarging brain metastases, and are not using corticosteroids for at least 7 days prior to trial treatment. This exception does not include carcinomatous meningitis which is excluded regardless of clinical stability
16. Known human immunodeficiency virus (HIV), hepatitis B or hepatitis C infection
17. Has received a live (attenuated) vaccine within 30 days prior to the first dose of investigational therapy(ies). Seasonal flu vaccines that do not contain live virus and COVID-19 vaccines are permitted
18. Has participated in another clinical trial of an investigational drug (or a medical device) within 30 days of study enrollment
19. Pregnant, breastfeeding, or unwilling to practice birth control during participation in the study
20. Any clinically significant psychiatric, social, or medical condition that, in the opinion of the Investigator, could increase subject's risk, interfere with protocol adherence, or affect a subject's ability to give informed consent.

### 2.3.3 Discontinuation of Subjects from treatment

Subjects MUST discontinue receiving APX005M for any of the following reasons:

- Disease progression by RECIST 1.1, or disease progression following treatment beyond progression
- Death
- Toxicity requiring discontinuation of investigational therapy(ies) as outlined in the dose modification guidelines
- Failure to recover from a disease or treatment-related AE to baseline or ≤ Grade 1 within 12 weeks of last dose of APX005M (except Grade 2 alopecia, Grade 2 fatigue or Grade 2 skin toxicity), unless the subject is benefiting from therapy and after discussion with and approval by Apexigen Medical Monitor (or designee)
- Failure to recover from an AE related to infusion reaction/cytokine release within 4 weeks of last dose of APX005M
- Inability to reduce corticosteroid to ≤10 mg of prednisone or equivalent per day within 12 weeks of last dose of APX005M
- Subject's decision to withdraw for any reason from study treatment (if subject withdraws from study treatment the subject should enter the Follow-up Period)
- Pregnancy
- Any clinical AE, laboratory abnormality or coincident illness which, in the opinion of the investigator, indicates that continued participation in the study is not in the best interest of the subject
- Requirement for alternative therapy
- Noncompliance with study procedures, including use of prohibited medications
- Subject is lost to follow-up
- Loss of ability to freely provide consent through imprisonment or involuntarily incarceration for treatment of either a psychiatric or physical (e.g., infectious disease) illness
- Study termination by Apexigen

The primary reason for treatment discontinuation will be documented in the eCRF.

### 2.3.4 Study treatment

#### 2.3.4.1 APX005M Administration

For Cohorts 1 and 2, APX005M is administered on Day 1 of each 3-week or 2-week treatment cycle. In Cohort 3 APX005M will be administered after each fraction of SBRT during the time of combination treatment.

The APX005M infusion time will be 60 minutes. Sites should make every effort to target infusion timing to be as close to 60 minutes as possible. A window between -5 minutes and +10 minutes is permitted.

The APX005M infusion can be interrupted in the case of infusion reaction. Once symptoms resolve, infusion should be restarted at 50% of the initial infusion rate (e.g., from 100 mL/hr to 50 mL/hr).

All subjects will be discharged from clinic after a clinical evaluation. Subjects should have stable vital signs including lack of orthostatic hypotension (systolic blood pressure >100 mmHg, or no lower than 10 mm from baseline) without IV hydration (no hydration for at least 2 hours prior to discharge), lack of hypoxia (oxygen saturation >90% without oxygen), temperature <38°C, and heart rate <110 beats/min. After discharge, all subjects should be monitored by a caregiver or by a healthcare professional for 24 hours after the first 2 infusions of APX005M and as clinically indicated thereafter.

APX005M and SBRT may be administered up to 3 days after the scheduled Day 1 of Cycle 2 and beyond in case of medical/surgical events, or logistical reasons not related to study therapy

Administration of APX005M will continue for up to 12 months or until criteria in [Protocol Section 3.2.6.1 \(Discontinuation of Subjects from Treatment\)](#) are met.

#### 2.3.4.2 Radiation Therapy

All subjects assigned to cohort 3 should be evaluated and treated by a local radiation oncologist. All radiation treatment will follow the standard guidelines for a SBRT treatment course. Each radiation therapy target lesion will receive up to a total of 3200 cGy in 4 fractions of 800 cGy, administered on the same day and prior to infusion of APX005M. Fractions will be delivered every 2 weeks with the requirement of a minimum of 4 field 3D conformal planning to meet dose constraints to limit normal tissue toxicity of organs at risk (OAR). The first target lesion and the subsequent target lesion will be identified by the treating investigator based upon considerations of clinical benefit and toxicity risk. The RT target lesions shall not be CNS metastases.

#### 2.3.4.3 Treatment beyond Progression

Accumulating evidence indicates that subjects with solid tumors treated with immunotherapy or the combination of immunotherapy with RT may derive clinical benefit despite initial evidence of progressive disease. Subjects will be permitted to continue treatment beyond initial RECIST 1.1-defined progressive disease (iUPD, [iRECIST]) as long as they meet the following criteria:

- Investigator-assessed clinical benefit, without rapid disease progression, or with disease progression based primarily on changes in lymph nodes appearance
- Subject continues to meet retreatment criteria
- Subject tolerates study treatment

- Subject has stable ECOG performance status
- Treatment beyond progression will not delay an imminent intervention to prevent serious complications of disease progression (e.g., CNS metastases).

The assessment of clinical benefit should take into account whether the subject is clinically deteriorating and unlikely to receive further benefit from continued treatment. All decisions to continue treatment beyond initial progression should be discussed with the Apexigen Medical Monitor (or designee), and an assessment of the risk/benefit of continuing with study therapy must be documented in the study records.

For subjects who stay on treatment beyond RECIST 1.1-defined progressive disease, all study procedures should be performed continuously, including tumor assessments.

Subjects will be discontinued from the treatment upon further evidence of disease progression, as described in the iRECIST guidelines by Seymour et al.

### 2.3.5 Replacement of Subjects

Enrolled subjects assigned to a specific cohort who do not receive APX005M or are not evaluable for tumor response will be replaced in that cohort.

The decision to replace subjects will be made by the Sponsor.

Details of the replaced subjects will be listed in the FSR.

**Note:** Apexigen decided on 02-Nov-2021 that no more subjects would be replaced.

### 2.3.6 Follow up

Subjects who discontinue APX005M will enter the Follow-up Period unless study treatment discontinuation is due to any of the following:

- Subject death
- Withdrawal of consent for all study procedures
- Initiation of any anticancer therapy (except for subjects continuing immediately following this study on a PD-1/PD-L1 containing regimen for whom the regimen and the response to that regimen should be documented)
- Subject is lost to follow-up
- Study termination by Apexigen.

Regular follow-up visits (or phone contact or chart reviews) should be scheduled every 3 months or more frequently if clinically indicated.

All AEs that are considered related to APX005M must be followed to resolution, stabilization, until improvement is not expected, 30 days after receiving the last dose of APX005M, death, or initiation of new anticancer therapy, whichever occurs first. Serious AEs (SAEs), pregnancies and AEs with potential immunologic etiology will be recorded and followed up to 90 days after the last dose of APX005M, death, or initiation of new anticancer therapy, whichever occurs first.

Subsequent anticancer regimen should be documented. For subjects, who switch to a PD-1/PD-L1 containing regimen immediately after study treatment the response to that regimen should be documented. Once this information is collected, a subject is considered off-study.

## 2.4 Modifications made in the Statistical Analysis Plan

The following modifications have been made to the analyses specified in Protocol Amendment 2 (28 December 2020):

### Replacement of subjects:

Apexigen decided that no more subjects would be replaced after 02-Nov-2021.

### Efficacy population definition:

The definition of the efficacy population has been updated.

#### Original definition:

Subjects evaluable for efficacy (tumor response) are defined as those who have at least one on-treatment (post baseline) tumor assessment.

#### Modified definition:

Subjects evaluable for efficacy (tumor response) are defined as those who have measurable disease and at least one evaluable (post-baseline) tumor assessment performed during the treatment period or within 30 days after the administration of the last dose of treatment.

#### Note:

If “Death” or “Clinical Progression” without confirmation has been reported as the end of treatment reason before the first scheduled tumor assessment (first tumor assessment will be evaluated approximately  $8 \pm 1$  week following the first dose of APX005M.), the subject will be included in this population.

Response for these subjects will be considered Not Evaluable.

### Per Protocol Population definition:

The definition of the Per Protocol population has been added for sensitivity analysis.

### Enrolled Population definition:

The definition of the Enrolled population has been added.

### Disease control rate:

This variable is not included in the analysis within the protocol, it has been defined in the SAP and will be shown in the tables

### Duration of Response and PFS

In addition to RECIST progressions and deaths, the clinical progressions have been considered an event in these analyses.

### Exploratory analysis

The duration of Stable disease will be provided as exploratory analysis.

## Subgroup analysis

Some subgroups analyses have been added.

- Steroids received during treatment.
- LDH pre-treatment values above the upper normal range vs. below upper normal range
- Elevated pre-treatment LDH and prior CTLA4

### 3. ANALYSIS POPULATIONS

The following analysis populations are described in the study protocol.

#### 3.1 Efficacy population

Subjects evaluable for efficacy (tumor response) are defined as those who have measurable disease and at least one evaluable (post-baseline) tumor assessment performed during the treatment period or within 30 days after the administration of the last dose of treatment.

**Note:**

If “Death” or “Clinical Progression” without confirmation has been reported as the end of treatment reason before the first scheduled tumor assessment (first tumor assessment will be evaluated approximately 8 ± 1 week following the first dose of APX005M.), the subject will be included in this population.

These subjects will be considered not evaluable for the response.

#### 3.2 Safety Population (SAF)

All subjects receiving any APX005M will be included in the safety population. The subjects will be analyzed in the received treatment group.

#### 3.3 Other analysis sets

##### 3.3.1 Screening population

The Screened population is defined as all screened subjects, including screening failures, who are in the database. A list will be included.

##### 3.3.2 Screening Failure population

The Screening Failure population is defined as all Screened Failure subjects. A list will be included, with the number of subject and why it is considered a screening failure.

##### 3.3.3 Enrolled (Intent-to-treat) population

The enrolled population is defined as all screened subjects that are assigned to a cohort.

##### 3.3.4 Per Protocol population (PP)

The Per Protocol population (PP) is defined as all the subjects of the efficacy population who do not meet one or more of the following criteria that will potentially impact the primary efficacy objective:

- Deviations for the inclusion or exclusion criterion.
- Use of prohibited and/or restricted therapies.
- Patients who have clinical progression without any evidence of pathological or imaging data.

To assess the deviations that may result in the exclusion of subjects from the Per Protocol population, these will be reviewed and approved by the sponsor before database lock for analysis.

The Per Protocol population will be used for sensitivity analysis of the efficacy endpoints and will be considered supportive.

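### The per-protocol set excludes subjects for an outcome, clinical progression without imaging, and no planned analysis tests the primary ORR in the conservative direction

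*SAP*

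**What the plan says.** SAP 3.3.4 defines the PP set as "all the subjects of the efficacy population who do not meet one or more of the following criteria". The list has three items: deviations from the eligibility criteria, use of prohibited or restricted therapy, and "Patients who have clinical progression without any evidence of pathological or imaging data". The next sentence speaks of "deviations that may result in the exclusion of subjects from the Per Protocol population". The set "will be used for sensitivity analysis of the efficacy endpoints and will be considered supportive".

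The efficacy population is handled differently. Under the note in SAP 3.1, if treatment ended for death or unconfirmed clinical progression before the first scheduled tumor assessment, "the subject will be included in this population". The matching note in SAP 2.4 adds: "Response for these subjects will be considered Not Evaluable". SAP 4.4.2.1 divides confirmed responders by everyone in the analysis set, so these subjects count as non-responders.

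SAP Table 1 assigns the primary ORR to the efficacy population and to PP only. SAP 3.3.3 defines a further set ("The enrolled population is defined as all screened subjects that are assigned to a cohort"), but Table 1 gives it no column. SAP 5.2 uses it for disposition counts and percentages.

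**The concern.** The first two PP criteria are departures from the protocol. The third is something that happens to the subject after treatment starts, and the SAP treats it as failure elsewhere: SAP 2.4 adds clinical progression as an event for duration of response and PFS. Excluding subjects for it selects the analysis set on outcome and takes out subjects whom the efficacy population keeps on purpose.

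What is at stake is the value of the sensitivity analysis. PP lies inside the efficacy population. Treated subjects with no evaluable scan for other reasons, such as toxicity or withdrawal, are already outside both sets. The sponsor also stopped replacing subjects on 02-Nov-2021 (SAP 2.3.5), twelve days after the last enrolment on 21-Oct-2021 (SAP 5.3.8), so later losses of this kind are not made up. No planned analysis shows what the ORR would be with those subjects counted as non-responders.

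The membership sentence adds a smaller difficulty. It admits subjects "who do not meet one or more of the following criteria that will potentially impact the primary efficacy objective", which can mean either that none of the three is met or that at least one is not met.

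**Working it through.** **Inputs.** Planned sizes and assumed responders come from SAP 5.1: 2/11 in each of Cohorts 1 and 2, and 3/18 in Cohort 3. The interval is the exact two-sided 90% Clopper-Pearson interval of SAP 5.3.2.1. The number of clinical progressors without imaging is not in the documents; I assume k = 1 to 3 removed per cohort.

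**The plan's own figure.** SE = sqrt(p(1 − p)/n). For 2/11, sqrt(0.1818 × 0.8182/11) = 11.6%. For 3/18, sqrt(0.1667 × 0.8333/18) = 8.8%. Both match SAP 5.1.

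**Reading 1: the criterion means no post-baseline imaging.** Such a subject cannot be a RECIST responder, so with x responders among n subjects the ORR moves from x/n to x/(n − k).

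| k removed | Cohorts 1 and 2 (90% CI) | Cohort 3 (90% CI) |
|---|---|---|
| 0 | 2/11 = 18.2% (3.3 to 47.0) | 3/18 = 16.7% (4.7 to 37.7) |
| 1 | 2/10 = 20.0% (3.7 to 50.7) | 3/17 = 17.6% (5.0 to 39.6) |
| 2 | 2/9 = 22.2% (4.1 to 55.0) | 3/16 = 18.8% (5.3 to 41.7) |
| 3 | 2/8 = 25.0% (4.6 to 60.0) | 3/15 = 20.0% (5.7 to 44.0) |

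With no responders the estimate stays at 0% and only the upper limit moves (0/11: 23.8%; 0/9: 28.3%).

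**Reading 2: the criterion also covers progression that was itself not imaged, in a subject with earlier scans.** The notes under SAP Table 4 say that clinical progression is not documented progression for best response, so an earlier confirmed response stands. SAP Table 5 lists clinical-only progression as an event for duration of response, which is calculated only in confirmed responders. The SAP therefore foresees such subjects. Dropping one responder gives (x − 1)/(n − 1): 2/11 becomes 1/10 = 10.0% (0.5 to 39.4), and 3/18 becomes 2/17 = 11.8% (2.1 to 32.6). To offset one lost responder, k further non-responders must also go, with (x − 1)/(n − 1 − k) ≥ x/n. For 2/11 this needs 10 − k ≤ 5.5, and for 3/18 it needs 17 − k ≤ 12, so k = 5 in both cases.

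**The membership sentence.** Three criteria give eight possible patterns. If PP requires that none is met, one pattern is admitted. If it requires only that at least one is not met, seven are admitted, and only a subject meeting all three is excluded. A subject with no deviation is admitted either way.

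**The missing conservative check.** As an illustration, suppose two further treated subjects in a cohort had no evaluable response. Counting them as non-responders, 2/11 becomes 2/13 = 15.4% (2.8 to 41.0), and 3/18 becomes 3/20 = 15.0% (4.2 to 34.4). Neither set assigned to the primary ORR in Table 1 would show this.

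**The case against.** The strongest reply is that the conservative handling is already in the primary analysis. Early deaths and clinical progressors stay in the efficacy denominator, PP is labelled supportive, and both results are reported, so a reader can see any difference. Subjects admitted to the efficacy population because of death are not named in the PP criterion and stay in PP unless another criterion applies. Protocol 5.3.4 expects clinical-progression determinations to be rare, so the count may be one or none. The study is exploratory with no test or success threshold, and the intervals above overlap almost entirely. All of this stands, and it limits the weight of the point.

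It can also be argued that a missing scan is a legitimate PP ground. Protocol 2.2 and 4.3 ask for an end-of-treatment assessment when treatment stops before the first scheduled scan. But Protocol 5.3.4 lets the investigator forgo further assessment when progression is evident, and the criterion is written in terms of progression rather than a missed assessment.

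A reader might infer two stronger things. One is that the exclusion can only raise ORR. The documents do not support that: ORR is unchanged with no responders and falls under Reading 2. The other is that the membership rule is reversed, so that PP would consist of subjects with deviations. It is ambiguous rather than reversed: both readings admit clean subjects, and the following sentence in SAP 3.3.4, together with SAP 5.2.1, makes exclusion the evident intent.

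Finally, the Enrolled set includes subjects who were never dosed, so leaving it out of the efficacy analyses is defensible. That bears on which extra set to choose, not on whether one is needed.

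**Conclusion.** The point holds as a defect in a supportive analysis. The third PP criterion selects on outcome and takes out subjects whom the efficacy population deliberately keeps as non-responders. Under its most natural reading, and with at least one responder, it raises the PP ORR by 1.8 to 6.8 percentage points in Cohorts 1 and 2 and by 1.0 to 3.3 points in Cohort 3. This rests on the planning response rates and on one to three subjects removed, which is an assumption. Under the wider reading the shift can be downward, so even its direction depends on a term that the SAP leaves undefined.

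A reader might go further and conclude that the primary ORR is biased by this rule. It is not: the primary estimate uses the efficacy population. The consequence is that the only sensitivity set for the primary ORR is a subset chosen partly on outcome, and the conservative direction goes unchecked.

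**What to change.** 1. Delete the third criterion in SAP 3.3.4, so that clinical progressors without imaging stay in PP as non-responders.
2. Define PP as subjects of the efficacy population who meet none of the remaining exclusion criteria. This removes the ambiguity.
3. Add to SAP Table 1 an ORR analysis in the Safety population (all subjects who received any APX005M), with missing or non-evaluable response counted as non-response. The Safety population suits this better than the Enrolled set because it leaves out subjects who were never dosed.

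The cost is a few words in the SAP, one extra table, and a slightly less favourable supportive ORR. The primary analysis does not change, and no new data are needed.
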